A Prospective, Open-Label Trial of MHNA-003, a Smartphone-Delivered Cognitive Behavioral Therapy (CBT) Treatment, in Adults with Symptoms of Tinnitus	
Protocol Number:	MHNA-003-001
Registration ID:	NCT05696158
Product:	MHNA-003-001
Sponsor:	Mahana Therapeutics, Inc.
Version and Date:	Version 1.0 14 November 2023

Background

Mahana[™] Tinnitus (MHNA-003) is a Digital Therapeutic (DTx) in development at Mahana Therapeutics. MHNA-003 provides CBT adapted for tinnitus via smartphone application.

CBT is a skills-based, present-focused, time-limited psychological therapy that examines thoughts, feelings, and behaviors which have an adverse impact on an individual's life, the context in which these occur, and the relationship among these factors. Within CBT, data driven strategies are then employed to systematically target these factors. CBT programs strive to build adaptive coping skills and interrupt problematic behaviors that are perpetuating the targeted symptoms (e.g., inactivity, negative self-referential cognitions, ruminations that maintain the depressive cycle, etc.). Decades of rigorous scientific evidence demonstrate the effectiveness of CBT for treating mood and anxiety disorders, substance abuse, and insomnia, as well as improving QoL and disease management among patients with chronic medical illnesses^{1,2}.

The efficacy of internet-based CBT programs for tinnitus is well documented. In a recent meta-analysis conducted by Beukes et al.,³ It was found that internet-based CBT programs demonstrated a moderate effect size in reducing tinnitus distress. This effect was observed in comparison to both active and inactive control conditions across nine Randomized Controlled Trials (RCT) involving 1,165 tinnitus patients.

Objectives

The purpose of this study is to assess the safety and clinical outcomes for MHNA-003 used together with routine care in adult patients aged 18 and older with tinnitus or ringing in the ears.

Product-specific feedback and usage data will be collected in order to inform further development of MHNA-003.

Given the pilot study's open-label, single arm design, study findings should be interpreted as signals to explore in future randomized-controlled trials rather than identifying definitive clinical significance.

Study Design

This is a prospective, open-label study of the mobile app MHNA-003.

Between 125 and 250 participants will be enrolled. All enrolled participants will receive MHNA-003 in addition to their routine care.

[figure not shown]
Safety and clinical outcomes assessments will be collected bi-weekly for a total of four data collection timepoints.

A study design schematic is provided in Figure 1 below.

¹ Hofmann, S. G., Asnaani, A., Vonk, I. J., Sawyer, A. T., & Fang, A. (2012). The efficacy of cognitive behavioral therapy: A review of meta-analyses. Cognitive therapy and research, 36(5), 427-440

² Dobson, D., & Dobson, K. S. (2018). Evidence-based practice of cognitive-behavioral therapy. Guilford Publications.

³ Beukes EW, Manchaiah V, Allen PM, Baguley DM, Andersson G. Internet-Based Interventions for Adults With Hearing Loss, Tinnitus, and Vestibular Disorders: A Systematic Review and Meta-Analysis. Trends Hear. 2019 Jan-Dec;23:2331216519851749.

All study activities are decentralized and will not require participants to visit a site in person. A centralized Principal Investigator and clinical study staff will conduct study activities remotely. Participants will complete all study activities remotely.

Measures

Primary outcomes are a change from baseline in Tinnitus Functional Index (TFI) and TFI responder rate at 6 weeks. A reduction of 13 points is considered clinically significant for the TFI.⁴

Eligibility

Participants must satisfy the following criteria before entering the study:

- 1. Participant scores \geq 25 on the Tinnitus Functional Index.
- 2. Participant has experienced symptoms of tinnitus for at least 3 months.
- 3. Participant is at least 18 years of age at the time of consent.
- 4. Participant resides in the United States.
- 5. Participant is able to speak, read, and understand English.
- 6. Participant has access to an iOS or Android smartphone with the ability to complete study tasks.
- 7. Participant is able to commit the time required to complete therapy modules and study assessments.

Participants who meet any of the following criteria will be excluded from participating in the study:

- 1. Participant scores ≥ 2 on item 9 (suicidal thoughts) of the Beck's Depression Index (BDI).
- 2. Participant has been hospitalized for psychiatric reasons within 12 months of screening.
- 3. Participant is currently enrolled in or plans to enroll in another clinical study that could impact outcomes of this trial.
- 4. Other exclusions may apply if determined by the clinical study team that participation may be impacted.

Sample Size

This study will enroll 125-250 total participants.

⁴ Meikle MB, et al. *Ear Hear*. 2012;33(2):153-76

Intervention

MHNA-003 is an investigational software as a medical device (SaMD) built for mobile usage.

MHNA-003 comprises five total sessions. Each session includes several lessons which provide components of cognitive behavioral therapy.

We recommend that participants complete one lesson of MHNA-003 per day. One lesson takes approximately 10-15 minutes. At the recommended pace the study sessions will take participants approximately 30 days to complete all lessons. This study protocol includes twelve additional days (42 total study days) to accommodate unanticipated interruptions to therapy progress.

MHNA-003 is available via a downloadable application for iOS and Android smartphones. Access to MHNA-003 and technical assistance will be provided to participants at no charge.

MHNA-003 is considered a non-significant risk (NSR) device. The risks associated with using MHNA-003 are akin to those associated with using a mobile app for 10-15 minutes per day.

Statistical Analysis

Analyses of feasibility and participant-reported clinical outcomes primarily rely on descriptive statistics. Inferential statistics are used to explore potential preliminary associations. All statistical analyses are performed using Stata 18.0 and focus on the intent-to-treat population.

Baseline demographics and participant characteristics are summarized using descriptive statistics. Specifically, means, standard deviations (SD), and ranges are assessed for continuous variables and assessment scores typically treated as continuous. Data are presented as mean ± SD. For categorical data, n's and percentages are calculated.

Statistical analysis techniques are employed to evaluate changes in patient-reported outcomes over time. Magnitude and statistical significance for change from baseline are tested using single factor mixed effects linear GLS regression modeling. This type of model is able to handle missing data due to attrition and can also be utilized for complete datasets. The need for random effects is tested in all cases using the Hausman comparison⁵ and Breusch and Pagan Lagrangian multiplier test.⁶ The Breusch-Pagan and Cook-Weisberg test for heteroscedasticity⁷ is also utilized. Mean, standard error of the mean, and 95% confidence intervals are calculated for changes from baseline. Wald chi-square tests assess the significance of changes from baseline over time.

Six-week responder rates are evaluated utilizing multiple imputation modeling to account for missing data. Responder rates are imputed in the ITT population utilizing logistic models. Four baseline factors are included in the imputation model: age, sex, baseline GAD-7 score, and baseline PHQ-8 score. It is possible that these help to describe relevant populations for level of outcome. In addition, program adherence is included as a covariate because outcome level is

⁵ Hausman JA. *Econometrica*. 1978;46:1251-1271.

⁶ Breusch TS & Pagan AR. *Econometrica*. 1979;47(5):1287-1294.

⁷ Cook RD & Weisberg S. Biometrika. 1983;70(1):1-10.

hypothesized to be related to program adherence. Sensitivity analysis is performed by removing the auxiliary variables from the imputation regression. Standard error of the mean and 95% CI are calculated for the responder rates.

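### The 6-week responder rate is imputed as a yes/no outcome with no TFI score in the model, which can bias it and leaves no ITT share of participants who worsened

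*Combined protocol and SAP*

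**What the plan says.** The Measures section names two primary outcomes: "Primary outcomes are a change from baseline in Tinnitus Functional Index (TFI) and TFI responder rate at 6 weeks". The next sentence gives the only threshold: "A reduction of 13 points is considered clinically significant for the TFI". A responder is never formally defined, but the natural reading is a fall of 13 or more points, and no reading makes a rise count.

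The Statistical Analysis section handles the two outcomes differently. Mean change comes from a mixed effects model on the scores: "Mean, standard error of the mean, and 95% confidence intervals are calculated for changes from baseline". The responder rate is multiply imputed: "Responder rates are imputed in the ITT population utilizing logistic models". The covariates follow: "Four baseline factors are included in the imputation model: age, sex, baseline GAD-7 score, and baseline PHQ-8 score", with program adherence added. A sensitivity analysis removes these auxiliary variables, and then "Standard error of the mean and 95% CI are calculated for the responder rates". No TFI score appears in the imputation model, and no category of worsening is defined, imputed or reported.

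Under Objectives, "The purpose of this study is to assess the safety and clinical outcomes for MHNA-003 used together with routine care". The same section calls the trial single-arm and says that "study findings should be interpreted as signals to explore in future randomized-controlled trials".

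**The concern.** Responder status is a function of two numbers, baseline TFI and week-6 TFI. When week 6 is missing, the participant's own TFI history is the most informative thing known about it. Baseline TFI is certain to exist, because entry requires a score of at least 25 and the other primary outcome is change from baseline. Interim scores may exist too: Study Design plans bi-weekly outcome assessments at four timepoints, without naming TFI. The imputation uses none of this.

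Two consequences follow.

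- Multiple imputation is valid when missingness depends only on what is in the model. If participants whose TFI is not improving leave more often, and the listed covariates do not fully capture that, dropouts are given too high a chance of response.
- An imputed yes/no status places each dropout among responders or non-responders. Unchanged and worsened are merged, so the ITT analysis cannot say what share got worse. With no comparator and safety within the study's purpose, that share is a useful descriptive result.

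**Working it through.** **Inputs.** From the documents: threshold of 13 points (reduction), entry TFI of 25 or more, n = 125 to 250, ITT population, and the five imputation covariates. The enrolment range has no calculation behind it, so there is no planned figure to reproduce. Assumed, because the documents give no values: TFI SD 20 and test-retest reliability 0.80 (central case), with the ranges shown below, and dropout of 18 to 20%.

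**Step 1: bias in the responder rate.** Let d be the dropout fraction. Then

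bias = d × (response probability imputed to dropouts − their true response probability).

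A simulation under assumed inputs, with d about 0.18 and dropout depending on interim TFI change, gave a rate 2 to 3 points too high without TFI in the model and no bias with it. By the formula, this corresponds to a gap among dropouts of 0.02/0.18 = 11 points to 0.03/0.18 = 17 points. At n = 125 it amounts to 125 × 0.02 = 2.5 to 125 × 0.03 = 3.75 participants wrongly counted as responders. For scale, the complete-data 95% half-width of a 50% rate is 1.96 × √(0.25/n), which is 8.8 points at n = 125 and 6.2 at n = 250. The bias is smaller than that, but it does not shrink as n grows. Its sign reverses if early improvers are the ones who leave.

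**Step 2: what a yes/no imputation loses.** The ITT worsening share is

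W = (1 − d) × W(observed) + d × W(missing).

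Imputed responder status tells us only that W(missing) lies between 0 and 1 − R(missing), where R(missing) is the response rate among dropouts. With d = 0.18 and R(missing) = 26.4% (the central case below with a mean shift of −5), W is left undetermined over a span of 0.18 × 0.736 = 13 points.

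**Step 3: how large worsening might be.** With SD of change s = SD × √(2(1 − r)) and mean shift m, P(fall ≥ 13) = Φ((−13 − m)/s) and P(rise ≥ 13) = Φ((−13 + m)/s). In the central case s = 20 × √0.40 = 12.65.

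| Mean shift | Improve by 13+ | Worsen by 13+ | Worsening, of 125 |
|---|---|---|---|
| 0 | 15.2% | 15.2% | 19 |
| −5, same for all | 26.4% | 7.7% | 10 |
| −5, as 40% at −20 and 60% at +5 | 33.0% | 16.0% | 20 |
| −10, same for all | 40.6% | 3.5% | 4 |

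With no shift, SD 18 to 22 and reliability 0.75 to 0.90 give 5.3% to 20.2% each way. Wider inputs give 0.3% (SD 15, 0.95) to 25.1% (SD 25, 0.70).

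**Step 4: the score model must contain baseline TFI.** In 2,000,000 simulated participants (mean 45, SD 20, reliability 0.80, entry score at least 25, no true change), 15.2% truly cross 13 points each way. Imputing week-6 scores without baseline puts 29.6% of imputed participants past −13 and 30.3% past +13; with baseline, both are 15.2%. At 20% missing, leaving it out gives 0.8 × 15.2 + 0.2 × 29.6 = 18.1% and 0.8 × 15.2 + 0.2 × 30.3 = 18.2%.

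**Step 5: precision of a worsening share (complete data).** At 3.5% of 125 the Wilson 95% interval is about 1.4% to 8.3%. Exact intervals are 1.8% to 10.2% for 6/125 and 2.5% to 8.2% for 12/250.

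**The case against.** A responder rate counts improvement by construction, and the plan contradicts nothing by using one. A reader might infer that counting only falls is itself an error, or that the plan hides worsening. The documents support neither. Rises enter the mean change, which is the other primary outcome; observed week-6 scores allow a complete-case count at any time; and findings are framed as signals for later randomised trials.

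The planned outputs also partly reveal worsening. In the mixture row above, a mean of −5 with 33.0% responders implies, under normality, s = 8/0.44 = 18.2 and hence 16.2% worsening, against a true 16.0%. This stands, but it depends on near-normal changes. It also fails when the mean is near −13: the responder rate is then 50% whatever the SD, while worsening runs from 0.5% (SD 10) to 14.9% (SD 25). Without normality, a mean of −13, SD 20 and 50% responders are compatible with anything from 0% to 34.5% worsening, although that is an extreme bound.

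Three further limits stand. The documents call 13 points clinically significant only as a reduction, so +13 is a mirror image that they do not endorse. They do not call TFI a safety measure, the content of the safety assessments is not described in the text, and the Intervention section classes the app as non-significant risk. Finally, program adherence is in the planned model and may absorb part of any link between dropout and TFI course, which would reduce the bias in Step 1.

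**Conclusion.** The point holds as an improvement to consider; the plan is not in error here. What is firm from the text is that the imputation model for a primary outcome lists no TFI score, although baseline TFI is necessarily available, and that imputed yes/no status cannot yield an ITT worsening share. What is conditional is the size: 2 to 3 points of upward bias with about 18% dropout that follows TFI change, and a worsening share that could plausibly be a few percent or well above 10%. All of these rest on assumed SD, reliability and dropout.

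A reader might go further and treat a worsening share as evidence of harm from the app, or as a measure of noise to subtract from the responder rate. Neither is supported. Without a control arm the share cannot be attributed to the app, and it equals the noise rate only if the mean does not shift.

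**What to change.** - Impute the week-6 TFI score. Use baseline TFI, any earlier on-study TFI scores (if TFI is collected at those timepoints), age, sex, baseline GAD-7, baseline PHQ-8 and program adherence.
- Define a responder explicitly as a reduction of 13 or more points, and derive status from the imputed scores.
- Keep the planned logistic imputation as a sensitivity analysis.
- From the same imputations, report descriptively the share worsening by 13 or more points, with a 95% CI pooled across imputations by a stated method suited to small counts. State that +13 mirrors the improvement threshold and is an assumption for the sponsor to justify, and that the share cannot be attributed to the app.

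The cost is a few sentences and slightly more analysis work, with no new data. The result then relies on a score model, and Step 4 shows the distortion if baseline TFI is left out of it. The worsening share will be imprecise if worsening is rare, and wider than the complete-data intervals in Step 5 once imputation is allowed for.

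### Does the lack of a written safety definition, summary and denominator leave the study's safety aim without a usable result?

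*Combined protocol and SAP*

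**What the plan says.** Objectives in the combined protocol and SAP states: "The purpose of this study is to assess the safety and clinical outcomes for MHNA-003 used together with routine care". Study Design adds: "Safety and clinical outcomes assessments will be collected bi-weekly for a total of four data collection timepoints". Intervention fixes the length of the study: "This study protocol includes twelve additional days (42 total study days) to accommodate unanticipated interruptions to therapy progress".

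Safety then drops out of the readable text. Measures gives only the main efficacy outcomes: "Primary outcomes are a change from baseline in Tinnitus Functional Index (TFI) and TFI responder rate at 6 weeks". Statistical Analysis begins "Analyses of feasibility and participant-reported clinical outcomes primarily rely on descriptive statistics" and goes on to baseline summaries, change from baseline and six-week responder rates. Two general statements come close to covering safety:

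- On the population: "All statistical analyses are performed using Stata 18.0 and focus on the intent-to-treat population". The intent-to-treat (ITT) population is not defined.
- On categorical data: counts and percentages are to be given, but this sits in the paragraph on baseline characteristics.

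Missing data are addressed for efficacy only, by the mixed model for change scores and by multiple imputation for response: "Responder rates are imputed in the ITT population utilizing logistic models".

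Figure 1, the design schematic, is not shown in the text available and might name a safety instrument.

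**The concern.** An aim that is stated and has data collected for it would normally have a planned summary. Here the readable text leaves four things open: what counts as a safety event, whether participants or assessments are counted, who is in the denominator, and how someone who never reports is treated. Different answers give different figures from the same data, and they could be settled after the data are seen.

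Non-reporting is a realistic prospect. All study activity is remote, and the plan itself expects attrition in the efficacy data. If silent participants were taken as event-free without comment, a low event percentage could reflect poor return of assessments rather than good tolerability.

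**Working it through.** The plan states no safety rate, dropout rate or safety-based sample size, so there is no plan figure to reproduce. The check asks how far the open choices could move a result.

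**Inputs from the documents:** 125 to 250 enrolled (Sample Size); four bi-weekly timepoints (Study Design); 42 study days (Intervention). **Assumed:** the share never reporting, 0 to 40%; 5 or 15 participants with an event.

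**Schedule.** 42/14 + 1 = 4, so days 0, 14, 28 and 42 fit, with three timepoints after baseline.

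**Zero events.** The percentage is 0 on any denominator, so the information lies in the number reporting, n. The exact two-sided 95% upper limit is 1 − 0.025^(1/n).

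| Enrolled | Never report (assumed) | n | Upper limit |
|---|---|---|---|
| 125 | 0% | 125 | 2.9% |
| 125 | 20% | 100 | 3.6% |
| 125 | 40% | 75 | 4.8% |
| 250 | 0% | 250 | 1.5% |
| 250 | 20% | 200 | 1.8% |
| 250 | 40% | 150 | 2.4% |

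**Five participants with an event (assumed).** Over all enrolled the percentage is 5/N, over reporters 5/n, and with every silent participant counted as an event (5 + N − n)/N.

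| N | n | Enrolled | Reporters | All silent counted as events |
|---|---|---|---|---|
| 125 | 100 | 4.0% | 5.0% | 24.0% |
| 125 | 75 | 4.0% | 6.7% | 44.0% |
| 250 | 200 | 2.0% | 2.5% | 22.0% |
| 250 | 150 | 2.0% | 3.3% | 42.0% |

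The two ordinary denominators differ by the factor N/n, which is 1.25 at 20% silent and 1.67 at 40%. The last column is a bound; the documents do not point to it as an estimate.

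**Counting unit.** Suppose 15 of 250 participants each have an event at one assessment and reporting is complete. That is 15/250 = 6.0% of participants (exact 95% CI 3.4 to 9.7%) and 15/(3 × 250) = 15/750 = 2.0% of assessments. The threefold gap needs at most one event counted per assessment and a per-assessment percentage that the documents never suggest, so it carries little weight.

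**What the plan would give by default.** Study Design has every enrolled participant receive the app in a single arm, so the natural reading of ITT is all enrolled. Applying the categorical convention to that group gives n (%) of participants with an event. Nothing in the text tells the analyst to code a missing safety report as no event. Silence in Measures is weak evidence of neglect, because that section is not an inventory: the GAD-7 and PHQ-8 scores used in the imputation model are not listed there either.

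**The case for a change.** The strongest case for acting is that the plan provides for missing efficacy data but not for missing safety data, in a remote study where some participants will stop responding. The ITT sentence does not say how a silent participant counts, and the remedy looks cheap: a definition and one descriptive table. With no events, a plausible result for this app, a bare zero says little unless the number reporting is given.

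The description of the gap stands, and so does the point that the number reporting has to accompany the result. Two stronger claims do not. The first is that the event definition will be chosen after the data are seen: assessments scheduled at set timepoints imply an instrument whose content exists beforehand, so the text supports only that it could be. The second is that a large part of the purpose has no result: safety data are collected and can be tabulated.

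The obvious remedy is also not clearly better than what analysts would do unprompted. A headline percentage limited to participants with at least one post-baseline assessment would leave out someone who reports harm directly to study staff and then withdraws before any assessment.

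**Conclusion.** No change to the plan is needed. The readable text has no safety-specific definition, summary, denominator or non-report rule, but this is missing detail, and no stated rule gives a wrong answer. Writing it down would record what a competent analyst would report anyway: participants with an event over all enrolled, with the number who returned safety assessments beside it.

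Under the assumed 0 to 40% non-reporting, the ordinary denominators differ by a factor of at most 1.67, and the zero-event upper limit rises by at most about 1.9 percentage points (4.8 − 2.9 at 125 enrolled). Objectives treats the findings as signals for later randomised trials, Intervention classes the app as non-significant risk, and no decision rule in the readable text depends on a safety percentage.

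This conclusion assumes that the bi-weekly safety assessment elicits events, which the readable text neither confirms nor rules out, and that the report shows how many participants responded. If the assessment did not elicit events, the problem would lie in data collection rather than in the analysis plan.

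### The imputation model for the six-week TFI responder rate, a primary outcome, lists no TFI score, and the planned sensitivity analysis could not reveal the bias this may cause

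*Combined protocol and SAP*

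**What the plan says.** Measures sets two primary outcomes: "Primary outcomes are a change from baseline in Tinnitus Functional Index (TFI) and TFI responder rate at 6 weeks". It treats a 13-point fall in TFI as clinically meaningful, but does not say outright that this is the responder cut-off.

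Statistical Analysis handles missing data differently for the two outcomes. For change in TFI it uses a mixed-effects regression, with the remark "This type of model is able to handle missing data due to attrition and can also be utilized for complete datasets". For the responder rate it uses multiple imputation: "Responder rates are imputed in the ITT population utilizing logistic models". The predictors are named: "Four baseline factors are included in the imputation model: age, sex, baseline GAD-7 score, and baseline PHQ-8 score". Adherence is then added: "In addition, program adherence is included as a covariate because outcome level is" thought to follow it. One check is planned: "Sensitivity analysis is performed by removing the auxiliary variables from the imputation regression".

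Two other places matter. Eligibility requires a TFI of at least 25, so baseline TFI exists for every participant. Study Design says: "Safety and clinical outcomes assessments will be collected bi-weekly for a total of four data collection timepoints". Over 42 days this reads as baseline and weeks 2, 4 and 6. That TFI is taken at each of them is an inference, because the schematic is not shown.

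**The concern.** Response at week 6 is a function of baseline TFI and week-6 TFI, so earlier TFI scores are the natural predictors of a missing response. The stated model leaves all of them out. Suppose response means a fall of at least 13 points and TFI is taken at weeks 2 and 4. Then a dropout whose TFI had fallen 20 points by week 4 and one whose TFI had risen 10 points receive the same imputed probability whenever age, sex, GAD-7, PHQ-8 and adherence match.

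Imputation of this kind is unbiased only if, given the listed variables, dropout is unrelated to the outcome. If people also leave because they are not improving, or because they already have, that condition fails.

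The plan expects some attrition, and Objectives presents the results as signals for later randomized trials. A responder rate that is several points off could mislead that planning, and the planned check would not flag it. The two primary outcomes would also rest on different missing-data assumptions, because the mixed model uses the observed TFI values and the imputation model does not.

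**Working it through.** The documents give no responder rate, dropout rate, SD or correlation, so there is no figure of the plan's own to reproduce. The text fixes the model; the size has to be illustrated under assumptions.

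**Inputs from the documents.** Predictors: age, sex, GAD-7, PHQ-8, adherence (Statistical Analysis). Entry TFI of at least 25 (Eligibility). Enrolment of 125 to 250 (Sample Size).

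**Assumed inputs.** Response is a TFI fall of at least 13 points. TFI is observed at baseline and weeks 2 and 4. True rate 50.1%. Baseline TFI has mean about 52 and SD about 18, truncated at 25. TFI is correlated with GAD-7 and PHQ-8, and response is related to adherence. Missing at week 6: 15%, 30% or 40%. Dropout log-odds are 0.4 to 1.0 per SD of less improvement at week 4, that is, odds ratios of e^0.4 = 1.5 to e^1.0 = 2.7. There were 400,000 simulated participants.

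**Formula.** In large samples the imputed rate is (1 − m)·C + m·P. Here m is the fraction missing, C the completers' response rate and P the mean imputed probability among dropouts. With D the dropouts' true rate, bias = m·(P − D).

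**Results at 30% missing (rate, %; true value 50.1).**

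| Dropout depends on | Plan | Plan + baseline TFI | Plan + all TFI |
|---|---|---|---|
| Listed variables only | 50.1 | 50.1 | 50.1 |
| Baseline TFI, log-odds 0.7 | 49.1 | 50.2 | 50.2 |
| Week-4 change, log-odds 0.4 | 53.4 | 53.4 | 50.2 |
| Week-4 change, log-odds 0.7 | 55.6 | 55.5 | 50.2 |
| Week-4 change, log-odds 1.0 | 57.5 | 57.3 | 50.2 |

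When dropout depends on week-4 change, the plan gives 51.8 to 53.8% at 15% missing and 54.6 to 59.9% at 40% missing.

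**The middle case in numbers** (30% missing, log-odds 0.7, completers' rate 56.1%):

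- Dropouts' true rate: D = (50.1 − 0.70 × 56.1)/0.30 = 36.1%.
- Rate the plan imputes to them: P = (55.6 − 0.70 × 56.1)/0.30 = 54.4%.
- Bias = 0.30 × (54.4 − 36.1) = 5.5 points.
- With all TFI added: P = (50.2 − 0.70 × 56.1)/0.30 = 36.4%.

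**Scale.** The complete-data 95% half-width at a 50% rate is 1.96·√(0.25/n): 8.8 points at n = 125 and 6.2 at n = 250. The bias is thus 5.5/8.8 = 63% to 5.5/6.2 = 89% of the half-width.

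**What the planned sensitivity analysis would show (rate, %; 30% missing).** The plan does not say which of the five count as auxiliary, so each reading is shown.

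| Predictors kept | Dropout on week-4 change (plan 5.5 too high) | Dropout on listed variables only (plan unbiased) |
|---|---|---|
| All five (plan) | 55.6 | 50.1 |
| Adherence only | 55.7 | 49.9 |
| Four baseline factors only | 56.0 | 52.0 |
| None | 56.1 | 51.8 |

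The biased case moves by at most 0.5 point, the unbiased one by up to 1.9. Agreement between the primary and sensitivity results therefore says nothing about this bias.

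**Second simulation, different inputs.** Pre-screen TFI means 45/41/37/34 at weeks 0/2/4/6, SD 22, correlations 0.68 to 0.86, adherence correlated 0.3 with improvement, and dropout also related to adherence (odds ratio 1.5 per SD lower).

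- 30% dropout, odds ratio 2: +3.5 points if a third of dropouts leave before week 2, +5.0 if all leave after week 4.
- 20–40% dropout, odds ratio 1.5 to 3: +1.3 to +10.5 points. At 10% dropout, odds ratio 1.2 to 3: 0.2 to 2.3.
- Early improvers leave (odds ratio 0.5, 20–40% dropout): −2.4 to −6.9.
- Dropout on adherence only: 0.0 to −0.2.
- Coverage of the plan's 95% interval in the 30%, odds ratio 2 case: 70–89% for n = 125 to 250. With all TFI in the same logistic model it is 94–96%, with bias of 0.4 point or less.

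**The case against.** The strongest reply is that the larger figures all need interim TFI, and the documents do not say that TFI is taken at weeks 2 and 4. Only baseline TFI is certain. If dropout depends on baseline TFI alone, the error across the simulations is about 0.4 to 3.5 points, below the sampling half-width. Adding only baseline TFI hardly helps when dropout follows early change (5.0 falls to 4.7 in the second simulation). This stands as a limit on size. Baseline TFI would still belong in the model.

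Second, adherence is already in the model and may stand in for TFI change. With its correlation with improvement raised from 0.3 to 0.5, the middle-case bias falls from about 5 points to 3.9–4.3; at 0.7 it falls to 2.4–2.8. So the planned covariate can roughly halve the bias, but does not remove it.

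Third, the plan speaks of logistic models in the plural and of auxiliary variables, which leaves room for unlisted terms. Nothing in the text puts TFI among them, but the full model should be written out.

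Fourth, the mixed model for TFI change uses observed scores and offers a partial cross-check. That is fair, but it estimates a mean change and does not correct the responder rate.

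Last, this is a single-arm pilot, analysed mainly descriptively, with no decision rule on this rate. That limits the severity, not the validity of the point.

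**Conclusion.** The point holds, in conditional form. The imputation model as written omits every TFI score for an outcome defined on TFI. The responder rate is unbiased if dropout depends only on the five listed variables. It is biased if dropout also depends on TFI beyond them, with a sign that depends on who leaves.

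At 30% dropout and an odds ratio near 2 per SD of less early improvement, two sets of assumptions put the bias at 3.5 to 5.5 points. It is smaller with less dropout or a closer link between adherence and improvement, and larger with heavier, more selective dropout. These sizes rest on an assumed true rate near 50%, a 13-point responder cut-off and interim TFI collection, none of which the documents state. The failure of the variable-removal check was seen under both sets of assumptions: in the second, removing all five variables moves the result by 1.8 points when the bias is 5.0 and by 1.5 when there is no material bias.

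This is a worthwhile improvement to a stated method and does not threaten the trial.

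**What to change.** - Keep the five listed variables. Add baseline TFI and every available interim TFI score to the existing logistic imputation model, imputing missing interim scores first. Write out the full model.
- State the responder definition.
- Keep the variable-removal analysis, and add one for dropout not explained by observed data, such as non-responder imputation or a delta adjustment. Adding TFI does not solve that problem. If dropout depends on the week-6 change itself (30%, odds ratio 2), the second simulation gives +6.8 points for the plan, +3.2 with TFI added and −9.0 with non-responder imputation. The last is therefore a bound, not a better estimate.
- Optionally, impute continuous TFI and derive response in each completed data set. With 20–40% dropout unrelated to outcome and n = 188, variance is 17–38% lower than under the plan, against 5–16% lower when TFI is simply added to the logistic model (same assumptions as the second simulation).

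The cost is SAP wording and a few lines of Stata code, with no new participants or assessments. If interim TFI is not collected, only baseline TFI can be added and the gain is smaller.
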